9. RESEARCH METHODS

9.1 Study design

This is a prospective, observational, exposure cohort study of pregnancy outcomes in women with asthma exposed to benralizumab anytime during pregnancy or within 8 weeks prior to Last Menstrual Period (LMP) compared to pregnancy outcomes in women with a diagnosis of asthma who are currently treated for asthma but who have not used benralizumab during pregnancy or within 8 weeks prior to LMP but have used other anti-asthmatic medications, (treated disease comparison group), and pregnancy outcomes in women not diagnosed with asthma who have not been exposed to any known teratogens but have potentially been exposed to non-teratogenic agents (non-diseased comparison group).

The study is conducted by the Organization of Teratology Information Specialists (OTIS) Research Center located at the University of California San Diego. The registry relies on voluntary reporting of pregnancy and exposures by women and health care providers who contact the North American OTIS network of teratogen information services as well as other sources of recruitment (see Section 9.2.1 for modalities of recruitment).

The study design is appropriate for the study objectives in that mothers are enrolled before the outcome of pregnancy is known, direct measures of relative and absolute risk can be computed, and a range of adverse pregnancy outcomes can be evaluated. The study design includes the identification of women with benralizumab exposure in pregnancy, and two appropriate comparison groups. Data obtained for the treated diseased group assists with evaluation of the contribution of the underlying maternal disease to adverse pregnancy outcomes, and provides an appropriate comparison group for the benralizumab-exposed cohort. This is essential, in that maternal asthma itself has been associated with a wide variety of adverse pregnancy outcomes (Murphy et al., 2011; J. A. Namazy et al., 2013; Rejno et al., 2014). The non-asthmatic comparison group allows for comparison of asthmatic to non-asthmatic women. If the distribution of underlying disease severity is similar in both the benralizumab and the treated disease group, this could further illuminate the potential contribution of the disease (and disease-severity) to outcomes.

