9.2 Setting

The study population consists of three cohorts of pregnant women (See Section 9.5 for sample size).

Participants will be recruited into the three cohorts concurrently, on the basis of the following inclusion/exclusion criteria:

Cohort 1: Benralizumab-Exposed

Inclusion Criteria:

- Currently pregnant women diagnosed with asthma who contact the OTIS Research Center and who have been exposed to benralizumab for any number of days, at any dose, and at

any time from 8 weeks before the first day of LMP up to and including the end of pregnancy.

- Eligible participants will be currently pregnant women who agree to the conditions and requirements of the study including the interview schedule and release of medical records.

Exclusion Criteria:

- Women who have had exposure to another biologic, used for any indication, anytime during pregnancy or within 8 weeks of LMP.
- Women will not be eligible for Cohort 1 if they first contact the OTIS Research Center after prenatal diagnosis of a major structural birth defect.
- Retrospective cases (outcome of pregnancy known prior to enrollment).
- Women who have enrolled in the current study with a previous pregnancy.

Cohort 2: Treated Diseased Comparison

Inclusion Criteria:

- Currently pregnant women diagnosed with asthma and exposed to asthma medications for any number of days, at any dose, and at any time from LMP up to the date of enrollment, who contact the OTIS Research Center but who were not exposed to benralizumab during pregnancy or within 8 weeks prior to LMP.
- Eligible participants will be currently pregnant women who agree to the conditions and requirements of the study including the interview schedule and release of medical records.

Exclusion Criteria:

- Women with exposure to benralizumab any time during pregnancy or within 8 weeks prior to LMP.
- Women will not be eligible for Cohort 2 if they first come in contact with the OTIS Research Center after prenatal diagnosis of a major structural birth defect.
- Retrospective cases (outcome of pregnancy known prior to enrollment).
- Women who have enrolled in the current study with a previous pregnancy.

Cohort 3: Non-Asthmatic Comparison

Inclusion Criteria:

- Currently pregnant women who contact the OTIS Research Center.
- Eligible women may potentially have been exposed to non-teratogenic agents during this pregnancy.

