9.3.3 Confounders and effect modifiers

The potential confounders/effect modifiers listed below will be considered in multivariable analyses, as well as others that are relevant to each of the study outcomes:

- Maternal and paternal age
- Previous pregnancy history: gravidity and parity, previous spontaneous abortions and elective terminations
- Maternal and paternal race/ethnicity, education, occupation, socioeconomic status
- Pre-pregnancy body mass index
- Previous preterm delivery
- Previous child with birth defect
- Maternal conditions: e.g., depression, diabetes
- Maternal exposures: gestational timing and dose of all over-the-counter and prescription medications, including all asthma medications used during pregnancy; vitamin and

mineral supplements, herbal products; illnesses; fever; vaccinations, travel outside of the U.S.

- Prenatal testing: ultrasound and other prenatal tests; timing in gestation and results
- Pregnancy complications: e.g., pregnancy induced hypertension, gestational diabetes
- Maternal lifestyle habits: cigarette smoking, alcohol consumption and illicit drug use
- Asthma related covariates: Asthma Control Test at each maternal interview, years since diagnosis of asthma, hospitalizations or unscheduled asthma visits for asthma exacerbations throughout pregnancy, use of systemic steroids for asthma exacerbations, and classification of asthma severity at enrollment based on women self-reported prescription classified by ([GINA guidelines, 2016](#)) guidelines.

Methods for identifying and controlling for these confounders and/or effect modifiers are described in Section 9.7.1. The Statistical Analysis Plan (SAP) will provide greater detail on the definitions of, the identification of and the controlling for confounders and/or effect modifiers.

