Preterm Delivery	Pregnancies enrolled prior to 37.0 weeks' gestation and ending in at least one live born infant. Excludes twins or higher order multiples due to inherent higher risk of preterm birth in multiples. Exposure can occur any time in pregnancy prior to the event.
Small for Gestational Age Infants	Pregnancies ending in at least one live born infant; excluding twins or higher order multiples due to the inherent higher risk of reduced birth size in multiples. Exposure can occur any time in pregnancy prior to the event.
Still birth	All pregnancies, excluding lost-to-follow-up. Exposure can occur any time in pregnancy prior to the event.
Elective Termination	All pregnancies, excluding lost-to-follow-up. Exposure can occur anytime in pregnancy prior to the event.
Postnatal Growth	Pregnancies ending in at least one live born infant with pediatric growth records available at approximately 1 year of age. Multiples are excluded. Exposure can occur anytime in pregnancy.

Coding of outcomes is performed by the study staff using the definitions provided in the protocol. Interview, diary, and examination data will be recorded on hardcopies of forms, medical records and medical record abstraction forms may be recorded on hardcopies or electronically; these records will be retained in the Coordinating Center. Data from all forms will be extracted and entered into a customized database located in the Coordinating Center. The data will be extracted and entered by trained study personnel with extensive experience with this type of information. Entries will be periodically reviewed for logical errors, and intake and outcome forms will be validated for data entry accuracy.

The primary source for information collected on demographics and exposures is by maternal interview, as the participant typically provides more accurate information than the medical records, especially in regards to non-prescription medications and any medications not taken as prescribed. Doses, dates, and timing of exposure are confirmed with medical records. If the medication is administered in the office, the medical record is the primary source; if the medication is administered at home and there is a discrepancy between the record and maternal report, the participant is contacted and asked about the discrepancy.

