9.6.2 Timings of assessment during follow-up

Table 7 Timing of cohort enrollment, interviews, medical record requests and review*

	Anytime in Pregnancy	20-22 weeks' gestation*	32-34 weeks' gestation	0-6 weeks post-delivery	0-12 months post-delivery
Contact / Referral	√				
Enrollment and Consent	√				
Intake Interview	√				
Interim Interview I		√			
Interim Interview II			√		
Outcome Interview				√	
Medical Record Release Forms Sent for Signature				√	√

*A participant may have anywhere from 1-3 interviews during pregnancy, with a minimum of 4 weeks between interviews. If a participant enrolls at 18 weeks, the 20 week interview will be scheduled at 22 weeks. If a participant enrolls between 19 weeks and 30 weeks, the next scheduled interview will be 32 weeks. If a participant enrolls at 30 weeks, the 32 week interview will be scheduled at 34 weeks. If a participant enrolls after 30 weeks, no additional interviews will be scheduled during pregnancy.

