9.7.2 Exploratory/sensitivity analyses

Exploratory analyses addressing potential effect modifiers such as Asthma Control Test measures of disease symptom control, and measures of asthma exacerbation will be addressed.

In addition, sub-analyses based on length and gestational timing as well as dose of exposure to benralizumab will be performed.

Stratified analyses based on prenatal diagnostic test performed prior to enrollment in the study will be conducted for the primary endpoint. The purpose of this analysis is to address the inherent bias in excluding women at the time of enrollment in the cohort study who have already received prenatal diagnosis of a major structural birth defects, but including women who have already had a normal result or prenatal diagnosis for major structural birth defects prior to enrollment. Therefore, the planned stratified analysis will compare the birth prevalence of major structural birth defects among the subset of women enrolled in the cohorts prior to prenatal diagnostic testing to detect structural defects (ultrasound for structure, chorionic villus sampling, amniocentesis), to the birth prevalence of major birth defects among the subset of women enrolled in the cohorts after prenatal diagnostic testing to detect structural defects.

Regarding asthma severity, the measures are only captured after enrollment, and in the exposed group only after being on treatment, so they would typically not be included in the analysis as adjustment factors as they could be mediators. However, descriptive analyses of the balance in cohorts on measures of disease severity are presented. Sub-analyses or

sensitivity analyses within disease severity categories can be performed, depending on the distribution of the covariates. This would be described in detail in the SAP.

Sub-analyses excluding chromosomal or known genetic anomalies (classified by study investigators as having a known genetic etiology) will also be conducted. Details will be provided in the SAP.

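### Women may enrol after growth restriction or threatened preterm birth is already recognised, and the safeguard in 9.7.2 against this kind of selection covers the primary endpoint only

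*Protocol*

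**What the plan says.** **Eligibility (Protocol 9.2).** For the exposed cohort: "Women will not be eligible for Cohort 1 if they first contact the OTIS Research Center after prenatal diagnosis of a major structural birth defect". Cohorts 2 and 3 carry the same bar. The only other outcome-related exclusion is a pregnancy whose outcome was known before enrolment. Neither rule covers an ongoing pregnancy with diagnosed growth restriction, ruptured membranes or preterm labour.

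**Timing of entry (9.6.2).** Table 7 places contact, enrolment and intake at any time in pregnancy. Late entry is foreseen: "If a participant enrolls after 30 weeks, no additional interviews will be scheduled during pregnancy".

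**Denominators (9.6.1, Table 6).** SGA: "Pregnancies ending in at least one live born infant; excluding twins or higher order multiples due to the inherent higher risk". The row has no entry rule. Preterm delivery: "Pregnancies enrolled prior to 37.0 weeks' gestation and ending in at least one live born infant". By contrast, spontaneous abortion is limited to women enrolled before 20.0 weeks.

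**Analysis (9.7.1).** SGA gets an unadjusted relative risk with exact intervals. Preterm delivery gets Kaplan-Meier estimates that allow for gestational age at entry.

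**Known selection (9.7.2).** The Protocol recognises a bias from prenatal results obtained before enrolment and responds: "Stratified analyses based on prenatal diagnostic test performed prior to enrollment in the study will be conducted for the primary endpoint". It plans nothing similar for SGA or preterm delivery.

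**Data available (9.3.3).** The covariate list includes "Prenatal testing: ultrasound and other prenatal tests; timing in gestation and results", and pregnancy complications.

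**The concern.** Section 9.1 justifies the design partly because "mothers are enrolled before the outcome of pregnancy is known". For SGA and preterm delivery that protection is weaker than it looks. Growth restriction can be seen on ultrasound before delivery, and membrane rupture or preterm labour comes before preterm birth. A woman who makes contact after such news is still pregnant and eligible, but her risk of the outcome is already well above average.

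Enrolment relies on women and providers choosing to contact a teratogen information service. If the share who do so after bad news differs between the exposed and treated-asthma cohorts, the ratio reflects who called as well as what the drug did. The allowance for entry time in the preterm analysis does not remove this: delayed-entry methods assume that entry is unrelated to imminent risk, and a call prompted by threatened delivery breaks that assumption. SGA has no entry-time method at all. The 10% change-in-estimate rule is aimed at confounders, not at entry prompted by the outcome.

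At stake is how the two secondary ratios are read in a study that relies on point estimates and intervals rather than tests.

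**Working it through.** **Inputs from Protocol 9.5.** Analysed pregnancies: 180 exposed and 270 treated-asthma comparators (90% of 200 and 300). Comparator risk p: 10% for SGA and 7% for preterm birth.

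**Inputs not in the Protocol, so assumed.** f and g are the shares of exposed and comparator pregnancies that entered after such a warning. q is the outcome risk in those women, taken as 30% to 70%.

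**Step 1: reproduce Table 5.** Two independent binomials are enumerated exactly at 180/270. P(observed RR > 1.5) is:
- SGA: 0.067 at true RR 1 and 0.878 at true RR 2 (Table 5: 0.07 and 0.88).
- Preterm: 0.103 and 0.823 (Table 5: 0.10 and 0.83).

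All 32 SGA and preterm cells agree within 0.02.

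**Step 2: model.** With a true RR of 1, the exposed risk is (1-f)p + fq and the comparator risk is (1-g)p + gq. The expected RR is their quotient.

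Examples with g = 0 and f = 5%:
- SGA, q = 30%: 0.95 x 0.10 + 0.05 x 0.30 = 0.110; RR = 0.110/0.10 = 1.10.
- SGA, q = 70%: 0.095 + 0.035 = 0.130; RR = 1.30.
- Preterm, q = 30%: 0.0665 + 0.015 = 0.0815; RR = 0.0815/0.07 = 1.16.
- Preterm, q = 70%: 0.0665 + 0.035 = 0.1015; RR = 1.45.

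**Step 3: results with g = 0 and q = 30-70%.**

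| Exposed share f | SGA RR | SGA P(RR>1.5) | Preterm RR | Preterm P(RR>1.5) |
|---|---|---|---|---|
| 0 | 1.00 | 0.07 | 1.00 | 0.10 |
| 2% | 1.04-1.12 | 0.08-0.13 | 1.07-1.18 | 0.14-0.21 |
| 5% | 1.10-1.30 | 0.12-0.27 | 1.16-1.45 | 0.20-0.42 |
| 10% | 1.20-1.60 | 0.18-0.57 | 1.33-1.90 | 0.32-0.77 |

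Section 9.5 puts the chance of an observed RR of 1.5 or more under no effect below 20%. For preterm birth, a one-sided 5% share reaches or exceeds that level.

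**Step 4: other patterns.** Equal shares (f = g) give an RR of 1.00. If the excess lies among comparators (f = 0, g = 5% to 10%), the RR falls to 0.91-0.62 for SGA and 0.86-0.53 for preterm, which could hide a harm.

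**Step 5: share needed for a spurious RR of 1.5.** f = 0.5p/(q-p).
- SGA: 0.05/0.60 = 8.3% to 0.05/0.20 = 25% (15 to 45 of 180).
- Preterm: 0.035/0.63 = 5.6% to 0.035/0.23 = 15.2% (10 to 27 of 180).

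The preterm figures are on the plain risk-ratio scale of Table 5. A delayed-entry estimate could differ, so they are indicative.

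**Step 6: what happens if only women with an adverse finding are dropped.** Assume a true RR of 1, SGA risk 10%, half of SGA detected before late entry, and 30% late entrants among exposed against 10% among comparators.
- Exposed: (0.70 x 0.10 + 0.30 x 0.05)/(0.70 + 0.30 x 0.95) = 0.085/0.985 = 0.0863.
- Comparators: (0.90 x 0.10 + 0.10 x 0.05)/(0.90 + 0.10 x 0.95) = 0.095/0.995 = 0.0955.
- RR = 0.0863/0.0955 = about 0.90.

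This rule removes women with bad scans and keeps those with reassuring ones, so it creates a bias of its own.

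**The case against.** The strongest case on the other side has four parts.

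**Entry is expected to be early and alike across cohorts.** Section 9.5 expects most women to enrol in the first trimester, before growth restriction or preterm labour could be diagnosed. Section 9.2.1 describes the comparators as ascertained in a similar way, and section 7 says that administration by injection helps identify exposed pregnancies early. This stands: it makes a large differential share less likely. It does not rule one out, because late entry is allowed and its frequency is not stated.

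**The direction is not known.** A reader might infer that women on a new biologic are more likely to call after bad news, so that the ratios are inflated. Nothing in the Protocol shows this. An excess among comparators is equally open and would push the ratios down.

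**The study remains prospective.** A reader might also infer that the design ceases to be prospective for these endpoints. That goes too far. SGA is defined on measurements at birth, known outcomes are excluded, and a prenatal suspicion is not the outcome. For preterm delivery, the 37.0-week limit and the entry-time method deal with late entry as such. What they leave open is entry prompted by the warning itself.

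**Detail can go to the SAP.** Covariate lists and sensitivity analyses may properly be set there. However, eligibility, the Table 6 denominators and the restriction of the 9.7.2 stratification to the primary endpoint are fixed in the Protocol, and the limitations in 9.9 do not mention this selection.

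**Conclusion.** The gap is real and modest. The Protocol recognises selection on prenatal information known before enrolment, addresses it for structural defects, and leaves SGA and preterm delivery open to the same kind of selection. SGA is the clearer case, with neither an entry limit nor an entry-time method.

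Bias arises only if such entry differs between cohorts; it can go either way, and the Protocol gives no basis for its size. With a one-sided share of about 2% the distortion is small. At 5% or more it could change how an observed ratio is read. These figures rest on assumed shares, an assumed outcome risk of 30-70% in the affected women, none among comparators and a true RR of 1. They show what is possible and do not establish that the ratios will be driven by late callers. A prespecified sensitivity analysis is a cheap and proportionate answer.

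**What to change.** 1. Keep the Table 6 denominators for the main SGA and preterm analyses.
2. In 9.7.2, with detail in the SAP, extend the analysis by pre-enrolment testing to SGA and preterm delivery as a prespecified sensitivity analysis in all three cohorts.
3. Define the restriction or strata by timing, not by result: enrolled before any growth-assessing ultrasound (SGA), or before a fixed early gestational week (both endpoints). The 20.0-week cut already used for spontaneous abortion is one candidate. Do not simply drop women with an adverse finding, for the reason shown in the last step of the working.
4. Show each ratio with and without the restriction, and report the distribution of gestational age at enrolment by cohort.

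The prenatal-test dates and results and the obstetric records already collected should suffice. Dates of complications are not listed explicitly and would have to come from those records.

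**Cost.** The restricted analysis has fewer pregnancies and wider intervals. If 10-30% of women are lost (assumed), P(observed RR > 1.5) at a true RR of 2 falls from 0.88 to 0.86-0.83 for SGA and from 0.82 to 0.81-0.77 for preterm. At a true RR of 1 it rises from 0.07 to 0.08-0.10 and from 0.10 to 0.11-0.14. The main analysis is unaffected.

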9.3.2 Outcome definitions

- **Major Structural Birth Defects:** a major structural defect is defined and classified using the CDC coding manual (CDC, 2007), as reported by the mother and validated through the medical record. The CDC coding manual is utilized to classify defects reported through the ongoing population-based Metropolitan Atlanta Congenital Defects Program (MACDP) and is based on agreed-upon criteria by CDC investigators for major structural defects regardless of etiology. Infant medical records are abstracted by the data coordinator, and reviewed by the study manager. Final validation of the classification of

all major birth defects reported in the study will be conducted by the OTIS Co-Investigator with expertise in the diagnosis of birth defects.

- **Preterm Delivery:** preterm delivery is defined as a spontaneous or induced delivery at <37 gestational weeks, reported by the mother and validated through the medical record. Please refer to Section 9.3.1 for further description of the method for defining gestational age and therefore preterm birth.
- **Small for Gestational Age (SGA) Infants:** Live born infants who are \leq 10th centile on birth weight, length and/or head circumference for infant sex and gestational age will be considered small for gestational age. The U.S. Centers for Disease Control and Prevention (NCHS) growth charts will be used for full term infants, and preterm growth charts will be used for preterm infants (Lubchenco, 1966). The outcomes of birth weight, length and head circumference are reported by the mother and validated through the medical record.
- **Spontaneous Abortion:** Spontaneous abortion is defined as spontaneous pregnancy loss prior to 20.0 weeks' gestation. In this study, since women enroll after recognition of pregnancy, spontaneous abortions are only identified after enrollment in clinically recognized pregnancies. This outcome is reported by the mother and validated through the medical record.
- **Stillbirth:** Stillbirth is defined as a fetal death that occurs \geq 20 weeks' gestation. This outcome is reported by the mother and validated through the medical record.
- **Elective Termination:** Elective termination is defined as deliberate interruption of pregnancy by surgical or medical means.

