9.6.1 Data handling conventions

Initial identification of major structural defects is performed by the study Data Coordinator, and then verified and classified by the Study Manager using the CDC coding manual (CDC, 2007). Final validation of the classification of all major birth defects reported in the study will be conducted by the OTIS Co-Investigator with expertise in the diagnosis of birth defects. All prenatal exposures to medications and vaccines are coded using the Slone Drug Dictionary (<http://sites.bu.edu/slone-drug-dictionary/>).

Twins or higher order multiples are handled as one pregnancy outcome. For example, if the pregnancy ends in at least one live born infant, the outcome is considered a live born outcome. If either or both twins have a major birth defect, the outcome is considered one major birth defect outcome. Twins are excluded from analyses of preterm delivery, small for gestational age infants, and postnatal growth.

Lost-to-follow-up status is designated if a participant withdraws from the study before the outcome of pregnancy is known or reported, or if study staff are unable to make contact with

the study participant within 12 months of the estimated end of pregnancy in order to obtain outcome information. Participants who are lost-to-follow-up but who have at least one day of follow-up after enrollment are included in time-to-event outcomes such as spontaneous abortion if they are otherwise eligible for inclusion in that analysis.

Table 6 Denominators by outcome

Outcome	Denominator
Major Structural Birth Defects Among Live Births	Pregnancies ending in live birth with exposure in the first trimester for benralizumab cohort, and other comparison groups at least one malformed infant in an individual pregnancy is considered one malformed outcome
Major Structural Birth Defects Among All Pregnancies	Pregnancies with any outcome excluding those lost-to-follow-up; with exposure in the first trimester for benralizumab cohort, and other comparison groups; at least one malformed fetus/infant in an individual pregnancy is considered one malformed outcome
Spontaneous Abortion	Pregnancies enrolled in the study prior to 20.0 weeks' gestation with at least 1 follow-up data collection point after enrollment date. Exposure can occur any time in pregnancy prior to the event.

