Elective Termination: The proportion of pregnancies ending in elective termination will be compared between the benralizumab exposed group enrolled prior to 20.0 weeks' gestation, and the diseased and non-diseased cohorts enrolled prior to 20.0 weeks' gestation.

Small for Age Postnatal Growth: After exclusion of twins or higher order multiples, the proportion of pregnancies ending in a live born infant \leq 10th centile of postnatal weight, length and/or head circumference will be compared between the benralizumab group exposed anytime in pregnancy and the treated diseased and non-diseased cohorts.

Statistical methods:

Descriptive tables will be prepared for characteristics of each of the cohorts in each interim and final report displaying n, means, standard deviations, minimums and maximums or proportions and percentages.

For the primary endpoint of major structural defects, and for the secondary endpoints of small for gestational age infants, postnatal growth and elective termination, un-adjusted relative risk estimates will be presented together with exact two-sided 95% and 80% confidence intervals.

For the secondary endpoints of preterm delivery, spontaneous abortion, and stillbirth, survival methods will be used (Kaplan Meier) to estimate crude rates and confidence intervals accounting for gestational timing of enrollment in the study.

Adjusted analyses producing relative risks and 95% and 80% confidence intervals or hazard ratios and 95% and 80% confidence intervals, where numbers permit, will be conducted. A minimum of 30 events in the overall analysis sample is required for adjusted analysis for those outcomes assessed with logistic regression. A minimum of 20 events in the overall analysis sample is required for adjusted analysis for those outcomes assessed with Cox Proportional Hazards.

Confounders will be considered for each adjusted analysis separately, using the method of change in estimate of the effect of exposure to benralizumab by 10% or more. If one confounder is identified, direct adjustment will be performed. However, given the expected low frequency of events in a study of this size, if two or more confounders are identified in any given analysis, a propensity score approach for adjustment will be considered. Appropriateness of models will be assessed graphically and by standard statistical methods.

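### Elective termination has two conflicting analysis sets, and under either one its crude relative risk ignores gestational age at enrolment

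*Protocol*

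**What the plan says.** **Elective termination**

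- *Definition, section 9.3.2:* "Elective termination is defined as deliberate interruption of pregnancy by surgical or medical means". No gestational limit is set.
- *Denominator, section 9.6.1, Table 6:* all pregnancies except those lost to follow-up, with no condition on when the woman enrolled. Apart from the spelling of one word, the row matches the stillbirth row quoted below.
- *Comparison, section 9.7.1:* the groups are "the benralizumab exposed group enrolled prior to 20.0 weeks' gestation, and the diseased and non-diseased cohorts enrolled prior to 20.0 weeks' gestation".
- *Estimator, section 9.7.1, statistical methods:* elective termination is listed with major defects, small for gestational age and postnatal growth, for which "un-adjusted relative risk estimates will be presented together with exact two-sided 95% and 80% confidence intervals".

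**Spontaneous abortion, for contrast.** Table 6 and section 9.7.1 both restrict to women enrolled before 20.0 weeks, and 9.7.1 requires the comparison to account for left truncation.

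**Stillbirth**

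- *Definition, section 9.3.2:* "Stillbirth is defined as a fetal death that occurs" at 20 weeks' gestation or later.
- *Denominator, Table 6:* "All pregnancies, excluding lost-to-follow-up. Exposure can occur any time in pregnancy prior to the event".
- *Estimator, section 9.7.1:* "For the secondary endpoints of preterm delivery, spontaneous abortion, and stillbirth, survival methods will be used (Kaplan Meier"), with crude rates that account for gestational timing of enrolment. The endpoint paragraph of the same section speaks only of a proportion.
- *Lost women, section 9.6.1:* participants lost to follow-up "who have at least one day of follow-up after enrollment are included in time-to-event outcomes". Spontaneous abortion is the example given, and the sentence adds the condition that they are otherwise eligible for that analysis.

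**The concern.** Two analysts who each follow the protocol would build different elective-termination datasets. Denominators differ by every woman enrolled at or after 20.0 weeks. Numerators can differ too: because the definition has no gestational limit, a termination in such a woman counts under Table 6 and is dropped under 9.7.1.

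The estimator raises a second problem that choosing one set does not settle. A woman can contribute a termination only if it happens after she enrols. Later enrolment leaves less time at risk, so a crude proportion partly measures when women joined. The protocol deals with this for spontaneous abortion but not for elective termination.

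The primary endpoint is major defects among live-born infants, so the termination comparison helps show whether pregnancies left that denominator at different rates by cohort. Section 9.5 sets observed ratios against thresholds of 1.2, 1.5, 2.0 and 3.0. An artefact of about 1.2 or 1.3 would fall on that scale.

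**Working it through.** The protocol states no rate or probability for elective termination or stillbirth, so it has no figure of its own to reproduce here. All enrolment shares and entry weeks below are assumptions.

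**1. Is Table 6 merely abbreviated?** Table 6 states an enrolment limit where one applies: before 20.0 weeks for spontaneous abortion and before 37.0 weeks for preterm delivery. Both agree with 9.7.1. The elective-termination row has no limit although 9.7.1 imposes one, so the difference is a real conflict.

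**2. Elective termination, Table 6 set, no drug effect.** Let f1 and f0 be the shares of exposed and comparator women enrolled at or after 20 weeks. Assume negligible terminations after 20 weeks and the same risk in women enrolled earlier. The expected crude ratio is (1 − f1)/(1 − f0).

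| f1 | f0 | Ratio |
|---|---|---|
| 0.30 | 0.10 | 0.70/0.90 = 0.78 |
| 0.10 | 0.30 | 0.90/0.70 = 1.29 |
| 0.40 | 0 | 0.60/1.00 = 0.60 |
| 0 | 0.40 | 1.00/0.60 = 1.67 |
| equal | equal | 1.00 |

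With both shares between 0 and 40%, the ratio lies between 0.60 and 1.67.

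**3. Elective termination, 9.7.1 set, no drug effect.** Restricting to enrolment before 20.0 weeks removes the component in step 2 but not differences in entry week before 20. Assume a constant hazard h = 0.02/14 per week, a total of 2% over weeks 6 to 20. For entry at week e, the risk observed is 1 − exp(−h(20 − e)).

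- Week 8: 1 − exp(−12h) = 0.0170
- Week 10: 1 − exp(−10h) = 0.0142
- Week 14: 1 − exp(−6h) = 0.0085
- Week 8 versus 10: 0.0170/0.0142 = 1.20, close to 12/10
- Week 8 versus 14: 0.0170/0.0085 = about 2.0, close to 12/6

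At low risk the ratio is close to the ratio of weeks at risk, so the assumed 2% hardly matters.

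**4. Stillbirth, does the same bias arise?** A simulation used a true hazard ratio of 1, losses before 20 weeks, entry uniform over weeks 6–14 in one cohort and 10–34 in the other, and a stillbirth risk inflated to about 10% for stability. The crude proportions were 0.0859 and 0.0754, a ratio of 1.14. The product-limit estimate with delayed entry gave 0.0955 and 0.0957, a ratio of 1.00. Removing pregnancies that ended before 20 weeks left those two estimates unchanged, because such pregnancies are in no risk set in which a stillbirth can occur.

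**5. Stillbirth, lost women.** Section 9.9 expects fewer than 5% lost. That is fewer than 0.05 × 200 = 10 exposed women and fewer than 0.05 × 300 = 15 in each comparison cohort.

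**The case against.** Several points on the other side have force.

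- **Enrolment timing may not differ.** The protocol nowhere says that it does. Section 9.2.1 describes comparators as similarly ascertained, and section 9.5 expects most women to enrol in the first trimester. This stands: the bias is conditional and its size is hypothetical. Against it, section 9.5 also expects some enrolment after 20 weeks, Table 7 allows enrolment at any time in pregnancy, and no matching on gestational week is described.
- **Section 9.7.1 already restricts to enrolment before 20.0 weeks.** This stands for the 0.78 and 1.29 figures, which belong to the Table 6 set only. It does not answer step 3.
- **Late enrollees are not outside the risk of termination.** A reader might infer that women enrolled at or after 20 weeks were never at risk. The definition sets no gestational limit, so they are better described as at low risk.
- **Stillbirth might seem biased in the same way**, because its Table 6 denominator counts pregnancies that ended before 20 weeks. The documents do not support that reading: 9.7.1 assigns stillbirth to survival methods that account for gestational timing of enrolment. Only a crude reading of the word proportion would bring the bias back.
- **The rule on lost women carries an eligibility condition.** The Table 6 exclusion could therefore be read as an outcome-specific exception to it. That is possible, but removing lost women from a survival analysis that can censor them sits poorly with the general rule, so the text needs clarifying.
- **This is a secondary outcome with no formal testing, and detail is left to the SAP.** True, but a SAP cannot follow both Table 6 and 9.7.1.

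**Conclusion.** The conflict between Table 6 and section 9.7.1 over the elective-termination set is certain and needs no assumption. It is also plain from the text that the unadjusted relative risk makes no allowance for gestational age at enrolment under either set.

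The size of any resulting bias is not known from the document. If terminations after 20 weeks are negligible and late-enrolment shares are 30% and 10%, the Table 6 set gives 0.78 or 1.29 with no drug effect, depending on direction. If the hazard is constant to week 20, the 9.7.1 set gives about 1.2 for a two-week difference in entry. If timing is equal, both give 1.

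For stillbirth the finding is limited to wording and to the handling of lost women, under 5% of participants by the protocol's own expectation. The point should be corrected, but it does not touch the estimator of the primary endpoint.

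**What to change.** **Elective termination**

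- Change the Table 6 row to pregnancies enrolled before 20.0 weeks, matching 9.7.1.
- In 9.7.1, move the outcome from the crude relative-risk list to the survival-method list, with entry at the enrolment week, left-truncated cumulative incidence, spontaneous abortion as a competing event, and lost women censored at last contact.
- State whether a termination after 20.0 weeks in a woman enrolled earlier counts, since the definition sets no limit.

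**Stillbirth**

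- Word the Table 6 denominator as pregnancies under observation at or after 20.0 weeks, so that it matches the delayed-entry Kaplan-Meier already planned.
- Replace the exclusion of lost women with censoring at last contact, in line with the general rule in 9.6.1.

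The cost is a few lines in Table 6 and 9.7.1 and a small programming change. No new data are needed, because gestational week at enrolment is already required for the spontaneous-abortion and preterm analyses.
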